8.2.2 Measurable Disease

Measurable lesions are defined as those that can be accurately measured in at least one dimension (longest diameter to be recorded) as ≥ 20 mm by chest x-ray, as ≥ 10 mm with CT or MRI scan, or ≥ 10 mm with calipers by clinical exam. All tumor measurements must be recorded in millimeters. NOTE: tumor lesions that are situated in a previously irradiated area might or might not be considered measurable. If the investigator thinks it appropriate to

include then, the conditions under which such lesions should be considered must be defined in the protocol.

Malignant Lymph Nodes

To be considered pathologically enlarged and measurable, a lymph node must be ≥ 15 mm in short axis when assessed by CT or MRI scan (CT scan slice thickness recommended to be no greater than 5 mm). At baseline and in follow-up, only the short axis will be measured and followed.

Non-measurable Disease

All other lesions (or sites of disease), including small lesions (longest diameter < 10 mm or pathological lymph nodes with ≥ 10 to < 15 mm short axis) are considered non-measurable disease. Bone lesions, leptomeningeal disease, ascites, pleural/pericardial effusions, lymphangitis cutis/pneumonitis, inflammatory breast disease and abdominal masses (not followed by CT or MRI) are considered as non-measurable. Non-measurable also includes lesions that are < 20 mm by chest x-ray. Cystic lesions that meet the criteria for radiographically defined simple cysts should not be considered as malignant lesions (neither measurable or non-measurable) since they are, by definition, simple cysts. 'Cystic lesions' thought to represent cystic metastases can be considered as measurable lesions, if they meet the definition of measurability described above. However, if non-cystic lesions are present in the same patient, these are preferred for selection as target lesions.

Target Lesions

All measurable lesions up to a maximum of 2 lesions per organ and 5 lesions in total, representative of all involved organs, should be identified as target lesions and recorded and measured at baseline. Target lesions should be selected on the basis of their size (lesions with the longest diameter), be representative of all involved organs, but in addition should be those that lend themselves to reproducible repeated measurements. It may be the case that, on occasion, the largest lesion does not lend itself to reproducible measurement in which circumstance the next largest lesion which can be measured reproducibly should be selected.

A sum of the diameters (longest for non-nodal lesions, short axis for nodal lesions) for all target lesions will be calculated and reported as the baseline sum diameters. If lymph nodes are to be included in the sum, then only the short axis is added into the sum. The baseline sum of the diameters will be used as reference to further characterize any objective tumor regression in the measurable dimension of the disease.

Non-target Lesions

All other lesions (or sites of disease) including any measurable lesions over and above the 5 target lesions should be identified as non-target lesions and should also be recorded at baseline. Measurements of these lesions are not required, but the presence or absence of unequivocal progression of each should be noted throughout follow-up.

8.2.3 Methods for Evaluation of Disease

Conventional CT and MRI

This guideline has defined measurability of lesions on CT scan based on the assumption that CT slice thickness is 5 mm or less. If CT scans have slice thickness greater than 5 mm, the minimum size for a measurable lesion should be twice the slice thickness. MRI is also acceptable in certain situations (e.g. for body scans).

Use of MRI remains a complex issue. MRI has excellent contrast, spatial, and temporal resolution; however, there are many image acquisition variables involved in MRI which greatly impact image quality, lesion conspicuity, and measurement. Furthermore, the availability of MRI is variable globally. As with CT, if an MRI is performed, the technical specifications of the scanning sequences used should be optimized for the evaluation of the type and site of disease. Furthermore, as with CT, the modality used at follow-up must be the same as was used at baseline and the lesions should be measured/assessed on the same pulse sequence. It is beyond the scope of the RECIST guidelines to prescribe specific MRI pulse sequence parameters for all scanners, body parts, and diseases.

Ideally, the same type of scanner should be used and the image acquisition protocol should be followed as closely as possible to prior scans. Body scans should be performed with breath-hold scanning techniques, if possible.

8.2.4 Methods for Evaluation of Bone Disease

Evaluation of Radionuclide Bone Scans: Bone disease will be evaluated using radionuclide bone scan. NOTE: Will follow PCWG3

Interpretation of serial changes in a radionuclide bone scan is well recognized to be highly subjective. Thus, the primary outcome will be whether the bone scan is stable or improved, vs. worse or progression. Changes in intensity will not be used as an outcome measure. The 2+2 rule will be applied for interpretation of bone scans:

Stable or Improved: Include the appearance of at least 2 new skeletal lesions on the first post-treatment scan performed 6 or more weeks later or changes in intensity of a preexisting lesion will be considered stable disease unless associated with other signs of progression.

Progression (Non-Response): Must be documented as the appearance of at least two additional new lesions on the next scan after the first 2 new lesions were noted. If at least two additional new lesions are seen on the next (confirmatory) scan the date of progression is the date of the first post treatment scan when the first two new lesions were documented. *An increase in the size or intensity of known skeletal lesions will not be considered progression.*

8.3 Response Criteria

8.3.1. Evaluation of Target Lesions

Complete Response (CR)

Disappearance of all target lesions. Any pathological lymph nodes (whether target or non-target) must have reduction in short axis to < 10 mm.

Partial Response (PR)

At least a 30% decrease in the sum of the diameters of target lesions, taking as reference the baseline sum diameters.

Progressive Disease (PD)

At least a 20% increase in the sum of the diameters of target lesions, taking as reference the smallest sum on study (this includes the baseline sum if that is the smallest on study). In addition to the relative increase of 20%, the sum must also demonstrate an absolute increase of at least 5 mm. NOTE: The appearance of one or more new lesions is also considered progression (see "Evaluation of New Lesions" below).

Stable Disease (SD)

Neither sufficient shrinkage to qualify for PR nor sufficient increase to qualify for PD, taking as reference the smallest sum diameters while on study. (Note: a change of 20% or more that does not increase the sum of the diameters by 5 mm or more is coded as stable disease)

To be assigned a status of stable disease, measurements must have met the stable disease criteria at least once after study entry at a minimum interval of 8 weeks.

In some circumstances, it may be difficult to distinguish residual disease from normal tissue. When the evaluation of complete response depends on this determination, it is recommended that the residual lesion be investigated (e.g., fine needle aspirate or biopsy) before confirming the complete response status.

Changes in nodal and visceral sites should be recorded and reported separately, and lymph nodes in the pelvis must measure at least 2 cm in greatest diameter to be considered target lesions. Complete elimination of disease at a particular site should be recorded separately. Any favorable change should be confirmed using a second follow-up scan.

8.3.2 Evaluation of Non-Target Lesions

Complete Response (CR)

Disappearance of all non-target lesions. All lymph nodes must be non-pathological in size (< 10 mm short axis).

Non-CR/Non-PD

Persistence of one or more non-target lesion(s) and/or the maintenance of tumor marker levels above the normal limits.

Progressive Disease (PD)

Appearance of one or more new lesions and/or unequivocal progression of existing non-target lesions (see "Evaluation of New Lesions" below). Unequivocal progression should not normally trump target lesion status. It must be representative of overall disease status change, not a single lesion increase.

When the patient also has measurable disease, there must be an overall level of substantial worsening in non-target disease such that, even in the presence of SD or PR in target disease, the overall tumor burden has increased sufficiently to merit discontinuation of therapy. A modest "increase" in the size of one or more non-target lesions is usually not sufficient to qualify for unequivocal progression status. The designation of overall progression solely on the basis of change in non-target disease in the face of SD or PR of target disease will therefore be extremely rare.

When the patient only has non-measurable disease, the increase in overall disease burden should be comparable in magnitude to the increase that would be required to declare PD for measurable disease: i.e., an increase in tumor burden from "trace" to "large", an increase in nodal disease from "localized" to "widespread", or an increase sufficient to require a change in therapy.

Although a clear progression of "non-target" lesions only is exceptional, the opinion of the treating physician should prevail in such circumstances, and the progression status should be confirmed at a later time by the review panel (or Principal Investigator).

8.3.3 Evaluation of New Lesions

The appearance of new lesions constitutes Progressive Disease (PD).

A growing lymph node that did not meet the criteria for reporting as a measurable or non-measurable lymph node at baseline should only be reported as a new lesion (and therefore progressive disease) if it:

- increases in size to ≥ 15 mm in the short axis, or
- there is new pathological confirmation that it is disease (regardless of size).
- new effusion or ascites that appears during treatment should only be reported as a new lesion (and therefore progressive disease) if it has cytological confirmation of malignancy.

8.3.4 PSA Response

As long as patient safety is the primary concern, in the absence of other indicators of disease progression, therapy should not be discontinued solely on the basis of a rise in PSA after week 8.

PSA progression is defined as the date that a 25% or greater increase and an absolute increase of 2.0 ng/mL or more from the nadir is documented and confirmed by a second value obtained 3 or more weeks later. Where no decline from baseline is documented, PSA progression is defined as a 25% increase from the baseline value along with an increase in absolute value of 2.0 ng/mL or more after 8 weeks.

8.3.5 Evaluating best overall response

The best overall response is the best response recorded from the start of treatment until either disease progression or recurrence. The investigator's determination of best overall response will be based both on response criteria and on confirmation criteria (Table 9). To be assigned a status of partial response or complete response, changes in tumor measurements must be confirmed by repeat assessment performed 4-6 weeks after the criteria for response are first met. To confirm stable disease, follow-up measurements must meet SD criteria at a minimum interval of 6-8 weeks after SD was first documented.

Note: If unconfirmed progression noted at the first time point is not confirmed at a second time point, the next assessment time point after the first that meets the criteria for progression will be treated as time point 1.

Table 9. Assessing Overall Response.

Target Lesions	Nontarget Lesions	New Lesions	Overall Response
CR	CR	No	CR
CR	Incomplete response/SD	No	PR
PR	Non-PD	No	PR
SD	Non-PD	No	SD
PD	Any	Yes or No	PD
Any	PD	Yes or No	PD
Any	Any	Yes	PD

Abbreviations: CR, complete response; PD, progressive disease; PR, partial response; SD, stable disease.

Subjects with global deterioration of health status who require treatment to be discontinued without objective evidence of disease progression should be classified as having symptomatic deterioration. Every effort should be made to document their objective progression, even after discontinuing treatment.

Subjects who do not have tumor response assessment due to rapid progression or toxicity will be considered nonresponders, will be included in the denominator for the response rate, and will be classified into one of the categories listed below:

- death attributed to disease progression
- early discontinuation attributed to disease progression
- death attributed to drug toxicity
- early discontinuation attributed to drug toxicity

Note: If a subject receives subsequent therapy before tumor progression is documented, the reason for changing therapy must be reported. Reasons include clinical progression, drug toxicity, or secondary therapy for maintaining tumor response.

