8.2 Therapeutic Response

Response and progression will be evaluated in this study using a combination of the revised Response Evaluation Criteria in Solid Tumors (RECIST 1.1) criteria¹⁵ and the guidelines for prostate cancer endpoints developed by the Prostate Cancer Clinical Trials Working Group (PCWG3).³

Trial objectives are defined based on controlling, relieving, or eliminating disease manifestations that are present when treatment is initiated, or preventing or delaying the development of disease manifestations that are expected to occur (or in some cases both). Identify whether control/relieve/eliminated or prevent/delay endpoints. Traditional measures of response reflect when a treatment is working and measures of progression indicate when a drug should be stopped. Because assessing response in bone (the most common site of prostate cancer spread) is uncertain and the clinical significance of PSA changes in response to therapy is not a reliable predictor of response, measures of response have been expanded in consortium trials to include measures of progression.

Patients will need to be reevaluated for response every cycle (or more frequently if indicated), according to the guidelines below.

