8.4 Confirmatory Measures/Duration of Response (see Table 10 for specific PCWG3 measures)

8.4.1 Confirming time-to-event outcomes

Any post-treatment change in disease status, be it favorable or unfavorable, should be confirmed using a second assessment at a later time 6-8 weeks.

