8.4.3 Progression-free survival

Progression-free survival (PFS) is a composite endpoint defined as the time from study entry or random assignment to disease progression in bone or soft-tissue, symptoms, or death. Use an interval-censored approach in which all assessments of the composite PFS endpoint (i.e., PSA, bone, CT scans, and symptom assessments) are performed at the same time points. All assessments of disease should be collected at the same time interval (e.g., bone scan, CT scan, and PSA at 12-week intervals). In addition to PSA, confirm post-treatment changes in measurable target lesions, radionuclide bone scans, and symptoms.

Table 10. Prostate Cancer Clinical Trials Working Group 3 (PCWG3) Outcome Measures.

Variable	Control/Relieve/Eliminate Endpoints	Prevent/Delay Endpoints
PSA	Record the percent change from baseline (rise or fall) at 8 weeks and, separately, the maximal change (rise or fall) at any time using a waterfall plot	Decline from baseline: record time from start of therapy to first PSA increase that is ~25% and ~2.0 ng/mL above the nadir, and which is confirmed by a second value 3 or more weeks later (i.e., a confirmed rising trend) † Recording the duration of PSA decline of little value No decline from baseline: PSA progression ~25% and ~2.0 ng/mL after 8 weeks
Soft-tissue lesions	Use RECIST with caveats: Only report changes in lymph nodes that were ~2 cm in diameter at baseline Record changes in nodal and visceral soft tissue sites separately Record complete elimination of disease at any site separately Confirm favorable change with second scan Record changes using waterfall plot	Use RECIST criteria for progression, with additional requirement that progression at first assessment be confirmed by a second scan 6 or more weeks later Note that for some treatments, a lesion may increase in size before it decreases
Bone	Record outcome as either new lesions or no new lesions First scheduled reassessment: No new lesions: continue therapy New lesions: perform a confirmatory scan 6 or more weeks later Confirmatory scan: No new lesions: continue therapy Additional new lesions: progression Subsequent scheduled reassessments: No new lesions: continue New lesions: progression	The appearance of ~2 new lesions, and, for the first reassessment only, a confirmatory scan performed 6 or more weeks later that shows at least 2 or more additional new lesions The date of progression is the date of the first scan that shows the change

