11.4 Analysis

11.4.1 For the Primary Objectives, all analyses point and (1-sided Wilson type 90% lower) CI estimates of the primary endpoint (PSA50) will be calculated.

Adverse events will be tabulated by incidence and severity graded according to the National Cancer Institute – Common Terminology Criteria for Adverse Events (CTCAE) version 4.03. Other statistics will include point and (2-sided) CI estimates of overall toxicity and of specific types of toxicity.

11.4.2 For Secondary Objective 1, descriptive statistics of TTPR will be used to summarize the time to PSA response. These descriptives will include N, median, mean, standard deviation (SD), interquartile range (IQR), minimum, and maximum.

11.4.3 For Secondary Objectives 2 and 3, the censored distributions of duration of response (RD) and PSA progression free survival (PFS) will be summarized with the Kaplan-Meier (K-M) survivorship estimate. A graph of the K-M curve for PRD and for PPFS will be generated along with the Hall-Wellner 90% confidence band, and a display of the number of patients at risk at several time points, below the X-axis. Summary statistics (6-month rate, 12-month rate, median, etc.) will be calculated from the K-M life table, each one with its respective 80% confidence interval (CI).

11.4.4 For the Correlative (Exploratory) Objectives, frequency distributions of all categorical variables (grade of specific types of toxicity, and categorical biomarkers or other correlatives) will be generated. Serial PSA levels will be displayed using spaghetti plots, and changes in PSA using waterfall plots.

Descriptive statistics will be used to summarize all continuous correlatives (e.g., PSA, continuous biomarkers and other correlatives), and changes in them pre/post ESK981 treatment. Gene expression levels will be \log_2 transformed prior to descriptive analysis. Multiple boxplots and scatterplots will be used to display summary statistics of biomarkers/correlatives and interrelationships between continuous correlatives, respectively.

Details of the planned determination of bioinformatics correlatives are given in Section 9. Response (whether PSA50 or overall), a categorical clinical outcome, will be statistically modeled as a function of each correlative using exact logistic regression. TTPR, a continuous

uncensored clinical outcome (limited to only the PSA50 responders), will be statistically modeled as a function of each correlative using linear regression.

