APPENDIX C: STUDY CALENDAR

	Screening	Treatment/Intervention Period					End of Tx (30 Days from last dose)	Follow-up Q 3 mos
		Cycle 1				Cycle 2 + beyond		
		Day -28 to Day -1	Day 1 (± 3 d)	Day 8 (± 3 d)	Day 15 (± 3 d)	Day 22 (± 3 d)	Day 1 (± 3 d)	
Informed consent and research authorization/ HIPAA form	X ^a							
Demographics, medical history, histologic and radiologic confirmation of disease	X							
Physical examination, vitals, weight, blood pressure	X	X	X	X	X	X	X	
EKG	X							
Height	X							
Performance status	X	X	X	X	X	X	X	
Concomitant meds	X	X	X	X	X	X	X	
Toxicity assessment	X	X	X	X	X	X	X	
Tumor measurements ^b	X	Tumor measurements will be repeated every 8 weeks (+/- 10 d)						
Laboratory tests ^c	X		X	X	X	X	X	
Correlative samples	X					X ^d	X	
Tumor Biopsies	X					X ^e		
Follow-up								X ^f

- a. May be obtained up to 60 days prior to initiation of study treatment.
- b. Radiographic evaluations will include a CT or MRI abd/pel and a bone scan or PET. Chest x-ray should be done if necessary for tumor assessment. Radiologic documentation will be provided for patients removed from study for progressive disease.
- c. Complete blood count, comprehensive chemistry panel including renal function (BUN, creatinine) and liver function tests (AST, ALT, total bilirubin), PSA, testosterone (at baseline).
- d. Whole blood samples will be collected every 4 weeks from screening to end of treatment (see lab manual).
- e. Tumor biopsies performed at the Cycle 3 visit (week 8, +/- 10 d) (see lab manual).
- f. Patients will be followed every three months for 5 years from end of treatment for survival and subsequent treatment.

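### Section 8.3.5 requires PR/CR to be confirmed at 4-6 weeks, which conflicts with the 6-8 weeks in 8.4.1 and with the 8-week scan calendar; best overall response and the exploratory models of overall response are affected

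*Combined protocol and SAP*

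**What the plan says.** The combined protocol and SAP gives several timings for confirming or repeating tumor assessments.

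- **Section 8.3.5** (best overall response): for PR or CR, changes in tumor measurements must be "confirmed by repeat assessment performed 4-6 weeks after the criteria for response are first met". This is mandatory.
- **Section 8.4.1**: any post-treatment change, favorable or not, "should be confirmed using a second assessment at a later time 6-8 weeks".
- **Section 8.3.1**: "Any favorable change should be confirmed using a second follow-up scan", with no interval. Table 10 likewise asks for a second scan for favorable soft-tissue change and gives no interval.
- **Appendix C**: "Tumor measurements will be repeated every 8 weeks (+/- 10 d". It shows no separate confirmatory scan.
- **Section 8.2**: "Patients will need to be reevaluated for response every cycle (or more frequently if indicated".
- **Section 8.4.3**: "All assessments of disease should be collected at the same time interval (e.g., bone scan, CT scan, and PSA at 12-week intervals".

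Stable disease has two rules. Section 8.3.1 requires the criteria to be met "at least once after study entry at a minimum interval of 8 weeks". Section 8.3.5 requires follow-up measurements that still meet the criteria at least 6-8 weeks after stable disease was first documented.

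On use, 11.4.4 states: "Response (whether PSA50 or overall), a categorical clinical outcome, will be statistically modeled as a function of each correlative". The method is exact logistic regression, under the correlative (exploratory) objectives.

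**The concern.** The one mandatory window, 4-6 weeks, closes two weeks before the next scheduled scan is due. The plan does not say that the next scheduled scan may serve as confirmation outside that window. Sections 8.3.5 and 8.4.1 also share only a single point, six weeks.

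Two analysts could therefore code the same patient differently. Take a patient with a PR at one scheduled scan that is still present 56 days later. Under 8.3.5 the response is unconfirmed; under 8.4.1 it is confirmed. The label feeds best overall response and the binary outcome in the exploratory models. In a trial of 27 evaluable and compliant patients (32 enrolled), moving even a few responders could change what those models can estimate.

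**Working it through.** The plan states no figure for how often a scheduled scan can serve as confirmation, so there is nothing to reproduce. The check compares the gap between consecutive scheduled scans with each window.

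**Inputs**
- Scan interval: 8 weeks = 56 days, window +/- 10 days (Appendix C).
- 8.3.5 window: 4-6 weeks = 28-42 days.
- 8.4.1 window: 6-8 weeks = 42-56 days.
- Assumption, not in the documents: each scan day is equally likely within its window.
- Appendix C does not say whether the window is tied to the calendar or counted from the previous scan, so both are shown.

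**Step 1: range of gaps (no timing assumption needed)**
- Tied to the calendar: gap = 56 + b - a, with a and b each from -10 to +10. Range 56 - 20 = 36 to 56 + 20 = 76 days.
- Counted from the previous scan: gap = 56 + b. Range 46 to 66 days.
- Both scans on time: 56 days. That is 56 - 42 = 14 days past the end of the 4-6 week window, and exactly on the upper limit of the 6-8 week window.

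**Step 2: share inside 28-42 days**
- Calendar, whole days: b - a must be -14 or lower. Of 21 x 21 = 441 pairs, 7+6+5+4+3+2+1 = 28 qualify; 28/441 = 6.3%.
- Calendar, continuous timing: 6²/(2 x 20²) = 36/800 = 4.5%.
- From the previous scan: the smallest gap is 46 days, so 0%.

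**Step 3: share inside 42-56 days**
- Calendar, whole days: b - a from -14 to 0 gives 7+8+...+21 = 210 pairs; 210/441 = 47.6%.
- Calendar, continuous: 0.50 - 0.045 = 45.5%.
- From the previous scan: 11 of 21 days = 52.4%.

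| Rule | Calendar windows | From previous scan |
|---|---|---|
| 4-6 weeks (8.3.5) | 4.5-6.3% | 0% |
| 6-8 weeks (8.4.1) | 45.5-47.6% | 52.4% |
| At least 4 weeks | 100% | 100% |

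The last row follows from Step 1: the smallest gap under either reading, 36 days, exceeds 28.

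**Step 4: sensitivity to timing.** If sites keep closer to schedule, the 4-6 week rule is met even less often. With calendar windows of +/- 7 days, gaps run 42-70 days and 1/225 = 0.4% qualify; with +/- 5 days, gaps run 46-66 days and none do.

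**Step 5: stable disease.** Counting from treatment start, an in-window first scan falls on days 46 to 66. On days 46 to 55 it misses the 8-week minimum in 8.3.1; from day 56 it meets it. The 8.3.5 rule counts from first documentation instead, and gives a range (6-8 weeks) as a minimum, so it does not say whether a 50-day gap is enough.

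**The case against.** **Other text could supply the confirmatory scan.** Section 8.2 calls for re-evaluation every cycle or more often, 8.3.5 itself calls for the repeat assessment, and nothing forbids an unscheduled scan. A site that reads these together could image at 4-6 weeks. This stands as a route to compliance, so the defect is not that confirmation is impossible. But if 8.2 means imaging every 28 days, it contradicts Appendix C. Even then, with the +/- 3 day visit window, gaps would run 22-34 days and only 28 of 49 pairs (57.1%) would reach 28 days.

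**Section 8.4.1 is workable.** A reader might infer that almost no scheduled scan can confirm a response under either rule. The documents do not support that: an on-time scan meets the 6-8 week window, about half of in-window scans do, and 8.4.1 says should rather than must.

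**Stable disease.** A reader might infer that patients with stable disease on schedule cannot be classified. That does not follow. A scan at day 56 or later meets the 8.3.1 minimum, and a patient first scanned at day 46 can qualify at a later scan. If study entry precedes treatment start, fewer first scans fall short. Only patients with no later qualifying scan are affected.

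**Impact.** A reader might infer that the response categories would be emptied or the trial's main result put at risk. Objective response is not a listed objective or endpoint; the PSA50 models in 11.4.4 are untouched; and 3.1.5 admits patients on PSA or bone progression alone, so target-lesion response may apply only to a subset. All of this stands and limits the point to exploratory work.

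**Conclusion.** The point holds in a limited form. The 4-6 week rule in 8.3.5 conflicts with 8.4.1 and does not fit Appendix C. Followed on the calendar, 0% to about 6% of consecutive scheduled scans can confirm a PR or CR under 8.3.5, against about 45-52% under 8.4.1. Most true responses would go unconfirmed under 8.3.5 unless a site adds a scan that the calendar does not list.

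The gap ranges (36-76 or 46-66 days) come directly from the documents. The percentages rest on even timing within the window. The plan gives no expected objective response rate, so the number of patients affected cannot be calculated.

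The consequence is confined to best overall response and the exploratory models of overall response. Sample size, the primary efficacy analysis and the secondary endpoints do not depend on it. The two stable-disease rules are a smaller inconsistency of the same kind.

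**What to change.** Settle the following before any response is coded.

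1. **Favorable change.** For coding best overall response, replace the 4-6 week (8.3.5) and 6-8 week (8.4.1) windows with one minimum interval that the next scheduled scan can meet. For example: confirmed at the next scheduled tumor assessment, at least 4 weeks after first documentation. Every in-window pair of scans satisfies this, and it agrees with 8.3.1 and Table 10, which ask for a second scan without an interval.
2. **Stable disease.** State one minimum with one anchor (treatment start or study entry) that is compatible with a first scan from day 46, in place of the two rules in 8.3.1 and 8.3.5.
3. **Progression.** Keep the separate confirmation rules for progression. The change to 8.4.1 should cover favorable change only.
4. **Schedule.** Reconcile the every-cycle re-evaluation in 8.2 and the 12-week example in 8.4.3 with Appendix C, saying which assessments involve imaging.

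The cost is wording only, with no added scans. The drawback is that confirmation comes at about 8 weeks rather than 4-6, so a response lost between those times would count as unconfirmed.
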